9.3. Sample Size and Accrual

In this exploratory pilot study, we will recruit 5 subjects in each of three age groups for a total of 15 subjects. The sample size is not justified because this is an exploratory pilot study that will yield data aimed to enable important future combined or comparative studies. We expect to complete the enrollment of study within 24 months.

If a physician committee member determines that they are no longer able to serve on the MC, the other committee members will be asked for recommendations for a replacement member, in consultation with PI. A replacement member will be identified, and the approval of NINDS will be sought prior to confirming the replacement.

In the event that the patient advocate representative makes the decision to step down, the board of the Glut1 Deficiency Foundation will be consulted, and a request for a replacement member will be made. The approval of NINDS will be sought prior to confirming the replacement of this committee member.

9.5. Data Analyses

Descriptive statistics will be computed for each group and combined age group in this pilot exploratory study. For normally distributed, continuous data, means and standard deviations will be used to describe the demographic and clinical characteristics of the patient population participating in the study. Medians, quartiles, and ranges will be used to describe characteristics of the patient population when the data are continuous, non-normally distributed. For categorical or dichotomous variables, the frequency or the proportion will be reported. The proportion of patients who do not alter EEG in subjects currently receiving the ketogenic diet will be computed along with the corresponding 95% confidence interval using the exact binomial method. The proportion of patients who have stable blood glucose and beta hydroxybutyrate levels during acute and long-term C7 supplementation will be computed using exact binomial method.

Paired t-tests or nonparametric one-sample signed tests will be conducted to test if there were significant changes in EEG and neurological performance indices such as ataxia in G1D patients receiving a normal diet between pre-C7 and post-C7. The objective of this study is to enable future combined or comparative studies to evaluate C7 comparability with the ketogenic diet by evaluating EEG and preservation of glycemia and ketosis. Descriptive statistics will be computed to inform (but not to determine; per the FOA) the sample size needed for a future larger study.

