late hepatic neoglucogenesis and this can decrease ketosis via insulin release (113). Neoglucogenesis stemming from heptanoate was observed by us after infusion of heptanoate in G1D mice (28). However, the relative amount of heptanoate infused was far greater than that used for G1D subjects. This was expected because a large quantity of labeled substrate is necessary to achieve labeling of brain intermediary metabolites in human and mouse ^{13}C NMR experiments as developed by us (27, 32, 114, 115). Thus, no significant neoglucogenesis (i.e., an increase in glycemia >10 mg/dl) is obligatorily anticipated after C7 ingestion.

Preliminary studies. One G1D subject has received C7 at 45% while on a 3.5:1 ketogenic diet without clinical or analytical consequence. Our 14 G1D subjects on a regular diet studied in the fasting state (8) exhibited a mean blood glucose of 88.5 ± 1.9 mg/dl (mean \pm SEM), which did not significantly change 30-60 min after ingestion of the base dose (35%) of C7 (87.8 ± 2.4 mg/dl). Beta- hydroxybutyrate levels were also unchanged (0.25 ± 0.10 mM in the fasting state relative to 0.23 ± 0.1 mM in the post-C7 state; mean \pm SEM). The same conclusion was reached after 10 of these subjects were tested after 3 months on C7. Thus, C7 metabolism does not appreciably interfere with glucose metabolism and related ketosis (beta-hydroxybutyrate) under a regular diet.

Fifteen subjects with G1D (five per each of three age groups) and currently receiving a ketogenic diet will participate. After baseline measurements of common blood analytes, EEG, and blood ketone body levels, subjects will be given triheptanoin dosed by individual daily caloric intake, divided in 4 daily fractionated doses.

All subjects will take triheptanoin for 24 hours (4 doses) on an inpatient basis.

This study, if the hypothesis is correct, will enable future combined or comparative studies because, for 1/3 of G1D patients, the ketogenic diet is insufficient and may be supplemented with C7 or replaced by it depending on future work, whereas, conversely, C7 may prove insufficient as first line therapy in some patients and necessitate the addition of a ketogenic diet.

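### Section 9.5 specifies no estimate of within-subject change in glucose or beta-hydroxybutyrate, although change is the stated secondary outcome and paired samples are collected

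*Combined protocol and SAP*

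**What the plan says.** The Synopsis lists the secondary outcome measures as changes in seizure rate, glycemia and ketosis. Section 3 plans random glucose and beta-hydroxybutyrate (BHB) at baseline, at four on-treatment times and at exit. Sections 6.2.2.2 and 6.2.2.3 place samples with the first C7 dose on Day 2, with the last dose that evening, on the morning of Day 3 and just before discharge.

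For these two analytes section 9.5 names one quantity: "The proportion of patients who have stable blood glucose and beta hydroxybutyrate levels", computed by the exact binomial method. A 95% level is stated for the EEG proportion ("along with the corresponding 95% confidence interval using the exact binomial method") and is not repeated for glucose and BHB.

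Three other sentences in 9.5 might be thought to cover change:

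- The paired tests: "Paired t-tests or nonparametric one-sample signed tests will be conducted to test if there were significant changes in EEG and neurological performance indices". They name neither glucose nor BHB, and they refer to patients on a normal diet.
- The summary statistics: "means and standard deviations will be used to describe the demographic and clinical characteristics of the patient population".
- The planning sentence: "Descriptive statistics will be computed to inform (but not to determine; per the FOA) the sample size needed for a future larger study". It names no variable.

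Section 9.5 does not define stability. Section 9.1 refers to normal laboratory ranges. Section 9.2.1.2 says new values will typically lie within 2 SD of previous values, using the laboratory's SD.

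**The concern.** An outcome defined as a change has no specified estimate of change. Reducing paired continuous values to a yes/no count discards the direction and most of the size information in them. It also yields no SD of change, which is what planning a later study on these variables would need.

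The stakes follow from the protocol's own rationale. Section 2.1 raises the possibility that C7 stimulates glucose production and thereby lowers ketosis, and it attaches a size to that: "no significant neoglucogenesis (i.e., an increase in glycemia >10 mg/dl) is obligatorily anticipated after C7 ingestion". No analysis in 9.5 shows how large a shift in glucose or BHB the data are compatible with, although the go/no-go decision in 9.1 rests partly on both being unaltered.

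**Working it through.** **The plan's own figure.** Section 9.3 states "we will recruit 5 subjects in each of three age groups for a total of 15 subjects", and 3 × 5 = 15. There is no power calculation to reproduce: "The sample size is not justified because this is an exploratory pilot study".

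**Step 1: the planned proportion.** When all n subjects are stable, the exact 95% lower limit is 0.025^(1/n).

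- 15/15: 0.025^(1/15) = 0.782, so 78.2% to 100%.
- 5/5 in one age group: 0.025^(1/5) = 0.478, so 47.8% to 100%.

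These are limits on a proportion, not on mg/dl or mM.

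**Step 2: what 15/15 says about size.** If 9.2.1.2 is used as a cutoff, at least 78.2% of changes lie within ±2 laboratory SD. That is more than half, so the median change lies there too. The laboratory SD is not given. Suppose it resembled the pre-C7 pilot SDs derived in Step 3 (assumption): the bound would be 2 × 7.11 = 14.2 mg/dl and 2 × 0.374 = 0.75 mM. If 9.1 is used instead, 15/15 sets no limit on change beyond the width of the normal range.

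**Step 3: inputs for a paired interval.** Section 2.1 gives mean ± SEM for 14 subjects, fasting and 30–60 minutes after C7, on a regular diet. SD = SEM × √14, with √14 = 3.742.

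- Glucose before: 1.9 × 3.742 = 7.11 mg/dl. After: 2.4 × 3.742 = 8.98 mg/dl.
- BHB before and after: 0.10 × 3.742 = 0.374 mM each.

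The pre/post correlation r is not in the documents and is assumed at 0, 0.5 and 0.8.

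**Step 4: half-widths.** SD of change = √(s₁² + s₂² − 2·r·s₁·s₂). Half-width = t(0.975, 14) × SD/√15 = 2.145/3.873 × SD = 0.554 × SD.

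| r | Glucose SD of change (mg/dl) | Half-width (mg/dl) | BHB SD of change (mM) | Half-width (mM) |
|---|---|---|---|---|
| 0 | 11.45 | 6.3 | 0.53 | 0.29 |
| 0.5 | 8.21 | 4.5 | 0.37 | 0.21 |
| 0.8 | 5.39 | 3.0 | 0.24 | 0.13 |

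Half-widths scale with the SD. At r = 0 with both SDs doubled, the glucose half-width is 2 × 6.34 = 12.7 mg/dl.

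**Step 5: how coarse the count is.** Take normally distributed changes, the Step 2 margins and r = 0.8. A true mean glucose shift of 7 mg/dl leaves each subject stable with probability 0.910, so 15/15 occurs with probability 0.910^15 ≈ 0.24. A BHB shift of 0.4 mM gives 0.929^15 ≈ 0.33. At r = 0.5 these fall to about 0.04 and 0.05, so the insensitivity depends on r.

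**The case against.** **The count suits the decision rule.** Section 9.1 counts subjects, at least 3 of 5 per age group, and compatibility is framed subject by subject. A mean near zero can hide some subjects losing ketosis while others gain. This stands: the proportion must remain a main analysis.

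**The plan does not exclude change summaries.** Section 9.5 promises descriptive statistics by group and overall, and again to inform a later study. This stands in part. The gap is one of specification: those sentences leave room for change scores, but name no change, baseline or interval.

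**Stronger readings that the documents do not support.** A reader might infer any of the following.

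- *A 15/15 result cannot bound the change at all.* Under 9.2.1.2 used as a cutoff it bounds the median change, though coarsely.
- *The paired data would bound the effect of C7.* The trial has one arm, and the samples are random draws at different times of day. An interval describes pre/post change, in which C7 is mixed with meals and time of day.
- *The trial would almost surely exclude a 10 mg/dl rise.* With the pilot SDs and no true change, the upper 95% limit falls below 10 mg/dl in about 88% / 99% / over 99% of trials (r = 0 / 0.5 / 0.8). With SDs 1.5 times larger this is about 56% / 83% / 99%, and with SDs doubled about 35% / 59% / 92%. The pilot subjects were fasting, on a regular diet and sampled within an hour of a 35% dose; this trial uses random samples, a ketogenic diet, 45% of calories and longer intervals. Nor is 10 mg/dl a trial margin: it appears in the rationale, and section 9 never adopts it.

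**Conclusion.** The point holds as a gap in specification. Section 9.5 attaches only a stable/not-stable proportion to two outcomes that the Synopsis defines as changes. It commits to no estimate, interval or SD of change for either, although the samples needed are already scheduled.

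The proportion limits (78.2% for 15/15, 47.8% for 5/5) are exact and rest on no assumption. The ±2 SD bound on the median depends on reading 9.2.1.2 as a cutoff, which its wording (typically) does not settle and which differs from 9.1. The half-widths in mg/dl and mM are illustrations only: they assume the pilot spread and a correlation that the documents do not report. The recommendation does not depend on them. In an exploratory study of 15 this is a cheap improvement that should be made, not a flaw that invalidates the plan.

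**What to change.** Add to section 9.5, for glucose and BHB:

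1. Each subject's change from a named baseline sample to the Day 2 bedtime value and to each Day 3 value. The Day 2 morning sample covers both analytes and can serve as baseline if it is drawn before the first dose. A Day 1 BHB baseline is unclear: section 6.3.10 lists BHB in the laboratory panel, the glucose/BHB row in section 6.1 starts on Day 2, and section 6.2.2.1 names only random glucose on Day 1.
2. The mean change (or median, if skewed) with a 95% confidence interval for all 15 subjects, the SD of change, and individual plots by age group.
3. The proportions stable, kept alongside and not demoted, with a single definition of stable that reconciles 9.1 and 9.2.1.2.
4. A statement that the interval describes pre/post change in a single arm with random samples at different times of day. The 10 mg/dl rise in 2.1 may be cited as a descriptive reference, not as a pass/fail margin.

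The cost is a few sentences and a small amount of analysis, with no new data. The downside is that the intervals may be wide, especially if spread in this trial exceeds the pilot's.

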1. STUDY OBJECTIVES

1.1. The main hypotheses tested are:

- C7 metabolism will not interfere with previously-acquired ketosis in G1D, as measured by no change in EEG from pre-C7 baseline.
- C7 metabolism will not interfere with previously-acquired ketosis in G1D, as measured by no increase in observable seizure rate and no clinically relevant changes glycemia and ketosis, as measured by random glucose levels and beta-hydroxybutyrate levels.

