4.2. Exclusion Criteria

- 4.2.1. Subjects with evidence of independent, unrelated metabolic and/or genetic disease.
- 4.2.2. Subjects with a chronic gastrointestinal disorder, such as irritable bowel syndrome, Crohn's disease, or colitis that could increase the subject's risk of developing diarrhea or stomach pain.
- 4.2.3. Subjects with a BMI (body mass index) greater than or equal to 30.
- 4.2.4. Subjects currently not on ketogenic diet.
- 4.2.5. Women who are pregnant or breast-feeding may not participate. Women who plan to become pregnant during the course of the study, or who are unwilling to use birth control to prevent pregnancy (including abstinence)

may not participate. Females age 10 and over will be asked to provide a serum or urine sample for a pregnancy test via dipstick. Subjects will be asked to

agree to abstinence or another form of birth control for the duration of the study.

4.2.6. Allergy/sensitivity to C7.

4.2.7. Previous use of triheptanoin less than 1 month prior to study initiation.

4.2.8. Treatment with medium chain triglycerides in the last 24 hours.

4.2.9. Subjects exhibiting signs of dementia, or diagnosed with any degenerative brain disorder (such as Alzheimer's disease) that would confound assessment of cognitive changes, in the opinion of the investigator.

4.2.10. Active drug or alcohol use or dependence that, in the opinion of the investigator, would interfere with adherence to study requirements.

4.2.11. Inability or unwillingness of subject or legal guardian/representative to give written informed consent, or assent for children age 10-17.

4.2.12. Addition of a new antiseizure drug in the previous 3 months.

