9.2. Outcomes

9.2.1. Primary outcome

9.2.1.1. EEG

C7 metabolism will not interfere with previously-acquired ketosis in G1D, as measured by no change in EEG from pre-C7 baseline.

Subjects receiving C7 supplementation will experience no interference with ketosis, as measured by no change in EEG.

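### Section 9.5 tests for a significant EEG change, which cannot support the stated hypothesis of no change, and it names patients on a normal diet, whom the trial excludes

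*Combined protocol and SAP*

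**What the plan says.** Section 1.1 gives the main EEG hypothesis as "C7 metabolism will not interfere with previously-acquired ketosis in G1D, as measured by no change in EEG from pre-C7 baseline". Section 9.2.1.1 repeats it as the primary outcome: "Subjects receiving C7 supplementation will experience no interference with ketosis, as measured by no change in EEG".

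Section 9.5 plans three things that bear on this:

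- **Descriptive summaries.** "Descriptive statistics will be computed for each group and combined age group in this pilot exploratory study".
- **Proportions.** The share of ketogenic-diet subjects whose EEG is unaltered, with an exact binomial 95% confidence interval, and the share with stable glucose and beta-hydroxybutyrate.
- **Tests.** "Paired t-tests or nonparametric one-sample signed tests will be conducted to test if there were significant changes in EEG", and also in "neurological performance indices such as ataxia in G1D patients receiving a normal diet between pre-C7 and post-C7".

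The exclusion criteria in Section 4.2 list "Subjects currently not on ketogenic diet". On size, Section 9.3 says "we will recruit 5 subjects in each of three age groups for a total of 15 subjects" and gives no justification for the number. Section 9.1 decides compatibility by counting: at least three of the five subjects in every age group must be unaltered. Section 9.2.1.2 gives a 2SD tolerance for glucose and beta-hydroxybutyrate. No tolerance for EEG is given, and no significance level or sidedness for the tests.

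**The concern.** The trial wants to show an absence of change. A paired t-test or sign test takes no change as its null hypothesis and asks whether the data contradict it. Failing to reject that null is not evidence for it, and failure becomes more likely as the sample shrinks or the EEG measure gets noisier. Small numbers and noise would then lean toward the conclusion hoped for.

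The protocol already reasons this way about earlier data. In Section 2.1, mean glucose in 14 subjects on a regular diet went from 88.5 to 87.8 mg/dl, "which did not significantly change 30-60 min after ingestion of the base dose (35%) of C7", and the paragraph concludes that C7 does not appreciably interfere with glucose metabolism. Nothing in Section 9.5 guards against the same step for EEG.

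The population named in the test sentence is a second, separate fault. As written, the tests apply to nobody in the trial. Correcting the population would still leave a test that cannot support the hypothesis.

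**Working it through.** The documents give no power, effect size, SD or significance level for these tests, so there is no figure of theirs to reproduce. The check asks how much a non-significant result would tell us.

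**Inputs.** n = 15 in total and 5 per age group (Section 9.3).

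**Assumptions.** Two-sided 5% level, in line with the 95% interval in Section 9.5; one-sided 5% is shown as the alternative. No EEG measure or SD is given, so changes are in units of d = true mean change divided by the SD of the paired differences, over a range.

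**1. Paired t-test.** Power = P(|T| > t(0.975, n−1)), with T noncentral t on n−1 degrees of freedom and noncentrality d√n. Critical values are 2.145 at n = 15 and 2.776 at n = 5. The chance of a miss is 1 − power.

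| d | Power, n=15 | Missed, n=15 | Missed at one-sided 5%, n=15 | Power, n=5 | Missed, n=5 |
|---|---|---|---|---|---|
| 0.3 | 19% | 81% | 71% | 8% | 92% |
| 0.5 | 44% | 56% | 42% | 14% | 86% |
| 0.8 | 82% | 18% | 10% | 28% | 72% |

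Two-sided power of 80% needs d = 0.78 at n = 15 and d = 1.68 at n = 5.

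**2. Sign test at n = 15, two-sided.**

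- 12 of 15 in one direction: p = 2 × (455 + 105 + 15 + 1) / 32768 = 0.035.
- 11 of 15: p = 2 × (1365 + 576) / 32768 = 0.118.

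So 12 of 15 are needed. If 70% or 80% of subjects truly change in the same direction, power is 30% or 65%.

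**3. Smallest attainable p at n = 5.** For both the exact sign test and the exact signed-rank test, the most extreme result gives two-sided p = 2 × (1/2)^5 = 0.0625. One-sided, it is (1/2)^5 = 0.031.

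**4. What an interval would show.** The half-width of the 95% interval for the mean change is t(0.975, n−1)/√n in SD units: 2.145/√15 = 0.55 at n = 15 and 2.776/√5 = 1.24 at n = 5.

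**5. Chance of concluding no change when the true change is zero, n = 15.** This is the probability that the whole interval lies within ± the tolerance (200,000 simulated trials, normal differences).

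| Tolerance (SD of differences) | One-sided 5% on each side (90% interval) | 95% interval |
|---|---|---|
| 0.5 | 20% | 7% |
| 0.8 | 81% | 64% |
| 1.0 | 96% | 90% |

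**The case against.** The strongest reply is that these tests decide nothing. Section 9.1 settles compatibility by counting unaltered subjects in each age group. Section 9.5 already plans the proportion with unaltered EEG, in the right population, with an exact interval that widens when numbers are small: 5 of 5 gives 47.8% to 100%. The study also calls itself an exploratory pilot. All of this stands, and it limits the consequence.

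Two stronger readings are tempting, and the documents support neither:

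- **That a non-significant test will be taken as compatibility.** No section says so. The Section 2.1 paragraph is background on regular-diet data and sets no rule for this trial. It shows only that the inference is a live risk.
- **That the nonparametric test can never be significant in a group of five.** This needs two-sided testing at 5% and testing within age groups. Section 9.5 states neither, and it promises by-group results for descriptive statistics only. At one-sided 5%, five of five in one direction would be significant, and at n = 15 the sign test can reach significance.

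It can also be said that the tests, as worded, do not cover the enrolled subjects and may have been left in by mistake. That is possible, but it makes the sentence a reason for correction. The exploratory label does not rescue the tests either, because Section 1.1 presents no change as a hypothesis to be tested.

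**Conclusion.** The concern holds as a mismatch between hypothesis and analysis. The only planned hypothesis tests on EEG can contradict no change but cannot support it, and they name a population that the trial excludes. At a two-sided 5% level with all 15 subjects, a non-significant t-test is weak evidence: a true mean change of half an SD would be missed more often than found. These sizes rest on an assumed level, sidedness and range of d. At one-sided 5% the misses fall to 71%, 42% and 10%, which does not alter the conclusion.

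The consequence is limited to interpretation and reporting. The go/no-go rule does not use these tests, and the planned proportion with its exact interval is unaffected.

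**What to change.** In Section 9.5:

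1. Name the enrolled ketogenic-diet subjects as the population.
2. Replace the significance tests with the paired change, post-C7 minus pre-C7, and its 95% confidence interval in the 15 subjects, reported beside the exact-interval proportion already planned.
3. State that a non-significant p-value is not evidence of no change.
4. Run no tests within age groups of five.
5. If a no-change conclusion on the mean EEG change is wanted, fix the EEG measure, the tolerance and the interval level before any EEG is read, and require the interval to lie inside the tolerance.

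For glucose and beta-hydroxybutyrate, keep the 2SD tolerance of Section 9.2.1.2. The 10 mg/dl figure in Section 2.1 is background, and using it as a margin would set up a competing criterion.

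Items 1 to 4 cost only wording. Item 5 needs an EEG measure, without which no tolerance can be set. It may well yield an inconclusive mean EEG change: with a 0.5 SD tolerance the chance of success under no true change is about 20% by the usual equivalence test, and lower if the 95% interval must fit. No new subjects or procedures are needed.
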